5.5 Correlative Studies

The goal of the planned laboratory correlative studies is to examine the relationship between presence of EBV infection and PD-L1 expression, to gain a better understanding of the impact of avelumab on the tumor's immunophenotype, and explore potential biomarkers which may correlate with response to avelumab.

5.5.1 Sample Collection Guidelines

Specimens should be collected as outlined below and ALL samples should be labeled with the following:

- Protocol number
- Institution
- Patient's de-identified study number
- Date of biopsy or surgery

5.5.1.1 Newly obtained tumor tissue

Newly obtained tumor tissue will be collected, preferably from a diagnostic core biopsy, within 42 days of initiating study treatment.

Samples collected for research will be obtained from only material in excess of that needed for routine clinical care as determined by a staff pathologist.

When possible, 4 core biopsies should be taken for lesions > 1.5 cm, otherwise 2 cores should be taken.

- If 4 cores are obtained, 1 core should be fresh frozen and the rest should be formalinfixed paraffin embedded (FFPE).
- If < 4 cores are obtained, tissue for research should be FFPE after being divided into the research and diagnostic documentation blocks according to the Pathology staff's specifications.

Ten (10) unstained sections (4-5 micron slices) or one (1) 20 micron roll-ups from FFPE tissue are desired.

Fresh frozen samples should be stored in liquid nitrogen and FFPE samples at room temperature until shipment.

5.5.1.2 Peripheral Blood Mononuclear Cells (PBMCs)

Blood for PBMCs will be collected prior to study treatment at screening (may be collected at the same time as blood drawn for routine laboratory tests).

Blood samples will be collected in two heparin green top tubes (approximately 20 ml).

Additional blood sample collections will be performed at:

• Twelve weeks after treatment initiation (+/- 7 days)

Samples should be processed the day of collection according to the PBMC isolation protocol in the Laboratory Manual.

PBMCs should be stored at -80°C until shipment.

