- 4. TSH monitoring will occur at baseline, cycle 2, cycle 4, then every 3 cycles thereafter (ie. Cycle 7,10 etc.), and at the end of treatment. For patients with asymptomatic TSH elevation, please refer to Section 4.3.1 for further evaluation. Specifically, if TSH < 0.5 x LLN, or TSH > 2 x ULN, or consistently out of range in 2 subsequent measurements: include T4 at subsequent cycles as clinically indicated; consider endocrinology consult.
- 5. Pregnancy test for females of child-bearing potential only.
- 6. Urinalysis (dipstick) will be performed at baseline, every 3 cycles following initiation of treatment (ie. Cycle 4, 7 and 10 etc.), and at the end of treatment. Urine microscopic examination should be performed if dipstick is abnormal.
- 7. EBV DNA plasma levels will be measured at baseline, every 3 cycles following initiation of treatment (ie. Cycle 4, 7, 10 etc.), and at end of treatment.
- 8. Newly obtained tumor tissue collection is mandatory upon study entry: See Section 5.5 for specifications. The study chair may grant exceptions to the mandatory biopsy should the treating physician deem that a biopsy is not feasible or unsafe for the patient, and archival tissue is available and provided for study purposes. A conversation with the study chair is required to obtain an exception. At time of disease progression, a repeat biopsy is encouraged but optional.
- 9. Blood for correlative studies should be collected at the same time blood is drawn for CBC and CMP if possible. 30 ml blood to be collected at baseline, at 12 weeks after treatment initiation (± 7 days). See Section 5.5.
- Imaging for radiographic disease assessment will be performed every 12 weeks following treatment initiation (± 7 days). The same imaging modality should be used throughout the study when feasible. For patients who are clinically stable, a repeat scan will be required 4 weeks (±7 days) after initial radiographic findings of disease progression as a confirmatory assessment. For CT or MRI, neck and chest should be evaluated; abdomen/pelvis as indicated. If a PET/CT is utilized, CT must be diagnostic quality.

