2.3 Endpoints

Primary Endpoint:

1. Overall response rate (defined as complete or partial response) at 6 months based on RECIST.

Secondary Endpoints:

- 1. Duration of response, defined as time from documentation of tumor response to disease progression
- 2. Progression-free survival, defined as the time start of Avelumab until disease progression or death
- 3. Overall survival, defined as the time from start of Avelumab to death from any cause

- 4. Toxicity (grade 3 or higher), as defined by CTCAE 4.03.
- 5. Exploratory correlatives:
 - Tissue (new biopsy required upon study entry prior to therapy; repeat biopsy at time of progression will be encouraged but optional):
 - PDL1 expression by immunohistochemistry (ABC technique [Vector labs], using rabbit mAb 1:200 [Cell Signaling])
 - Immunophenotyping by flow cytometry:
 - T cell subsets (CD4, CD8, FOXP3)
 - Macrophages (CD68)
 - Cytokeratin 5/6 (by immunohistochemistry)
 - Peripheral blood (comparison of baseline and 12 week post-treatment samples, unless otherwise denoted)
 - TCR and BCR sequencing
 - T cell subsets (CD3, CD4, CD8, CD25, FOXP3)
 - B cells (CD19, CD20)
 - Macrophage I/II and myeloid-derived suppressor cells (MDSC) (CD16, CD68, CD206)
 - Natural killer cell activity (CD56, CD16)
 - EBV DNA plasma levels (will be performed at baseline, every 12 weeks after treatment initiation and at end of treatment)
- 6. Clinical activity of Avelumab as defined by overall response rate will also be measured utilizing immune-related RECIST.

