3.2 Exclusion Criteria

Patients meeting any of the exclusion criteria at baseline will be excluded from study participation.

- 1. Patient is currently receiving or has received another investigational agent within 4 weeks prior to Day 1 of study.
- 2. Patient has received chemotherapy or radiotherapy within 4 weeks prior to Day 1 of study. Prior palliative radiotherapy to metastatic lesion(s) is permitted, provided there is at least one measurable lesion that has not been radiated.
- 3. Patient has received prior immunotherapy with inhibitors of PD-1/PD-L1 axis.

- 4. Patient has had major surgery or insufficient recovery from surgical-related trauma or wound healing within 14 days of Study Day 1.
- 5. Patient has had a prior Grade ≥ 3 immune-related adverse event (irAE) while receiving any previous immunotherapy agent, or any unresolved irAE > Grade 1.
- 6. Patient has a known additional malignancy that is progressing or requires active treatment. Exceptions include basal cell carcinoma of the skin or squamous cell carcinoma of the skin that has undergone potentially curative therapy or *in situ* cervical cancer.
- 7. Patient has known active central nervous system (CNS) metastases and/or carcinomatous meningitis.

Note: Patients with previously treated brain metastases may participate provided they are stable (without evidence of progression by imaging for at least four weeks prior to the first dose of trial treatment and any neurologic symptoms have returned to baseline), have no evidence of new or enlarging brain metastases, and are not using steroids for at least 7 days prior to trial treatment. This exception does not include carcinomatous meningitis which is excluded regardless of clinical stability.

 Patient has an active autoimmune disease that has required systemic treatment in the past 2 years (i.e. with use of disease modifying agents, corticosteroids or immunosuppressive drugs).

Notes:

- Patients with vitiligo, Grave's disease, or psoriasis not requiring systemic treatment within the past 2 years are not excluded.
- Replacement therapy (e.g., thyroxine, insulin, or physiologic corticosteroid replacement therapy for adrenal or pituitary insufficiency, etc.) is not considered a form of systemic treatment.
- Patient has a diagnosis of immunodeficiency, or is receiving systemic steroid therapy (>10mg prednisone daily, or steroid equivalent) or any other form of immunosuppressive therapy within 7 days prior to the first dose of avelumab.

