5.2 Screening/Baseline Procedures

Assessments performed exclusively to determine eligibility for this study will be done only after obtaining informed consent. Assessments performed for clinical indications (not exclusively to determine study eligibility) may be used for baseline values even if the studies were done before informed consent was obtained.

All screening procedures must be performed within 21 days prior to registration unless otherwise stated. The screening procedures include:

- Written informed consent (within 28 days).
- Review of inclusion and exclusion criteria.

- Complete medical/oncology history.
- Demographics.
- Documentation of concomitant medications.
- Complete physical examination, including vital signs and height.
- Performance status assessment.
- Laboratory tests (within 7 days; pregnancy test within 72 hours).
- Blood collection for EBV DNA plasma levels and correlative studies.
- Documentation of tumor staging (imaging completed within 28 days).
- Tumor biopsy tissue collection for correlative studies (within 42 days).

5.3 **Procedures During Treatment**

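### Baseline correlative blood is timed from registration and the washout from Day 1, so the exploratory before/after immune comparison can partly reflect recovery from prior therapy

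*Combined protocol and SAP*

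**What the plan says.** **Draw.** Section 5.5.1.2 states "Blood for PBMCs will be collected prior to study treatment at screening". Section 5.5.1.3 sets the same timing for the buffy coat used for TCR and BCR sequencing. Section 5.2 gives the default: "All screening procedures must be performed within 21 days prior to registration unless otherwise stated". Its list includes "Blood collection for EBV DNA plasma levels and correlative studies" with no window of its own, whereas routine bloods have one: "Laboratory tests (within 7 days; pregnancy test within 72 hours". The Schedule of Events marks both draws under screening and then at Cycle 4, not at Cycle 1. Section 5.3.1 schedules CBC and CMP on Cycle 1 Day 1 but no correlative or EBV DNA blood.

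**Preferred timing.** Schedule footnote 9 says "Blood for correlative studies should be collected at the same time blood is drawn for CBC and CMP if possible". Sections 5.5.1.2 and 5.5.1.3 only permit this. Footnote 7, on EBV DNA, is silent.

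**Washout.** Section 3.2, item 2, excludes a patient if "Patient has received chemotherapy or radiotherapy within 4 weeks prior to Day 1 of study".

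**Use.** Section 2.3 lists the peripheral blood markers among the exploratory correlatives, with a "comparison of baseline and 12 week post-treatment samples". EBV DNA is serial: baseline, every 12 weeks and end of treatment. Section 9.6 plans association tests, Kaplan-Meier, Cox and logistic models and descriptive summaries. It has no term for time since prior therapy.

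**The concern.** The washout is what would make the first sample a fair picture of the patient off treatment. Here it protects the first dose and not the sample. Every patient has had systemic therapy in the recurrent or metastatic setting (Section 3.1, item 4), so recent cytotoxic exposure is plausible, though its frequency is not stated.

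The trial has no control arm. If lymphocyte, NK or myeloid subsets, or the receptor repertoire, are still recovering at the draw, their return to normal by week 12 adds to any avelumab effect and cannot be separated from it. The interval from last therapy to draw will also differ between patients, which can blur the models in Section 9.6 that use baseline markers as predictors.

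At stake is the reading of the pharmacodynamic and biomarker results, not the decision on efficacy.

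**Working it through.** The documents state no interval from last therapy to baseline draw, so there is no figure of the plan's own to reproduce. The check is date arithmetic.

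**Inputs**
- Washout: 4 weeks = 28 days before Day 1 (Section 3.2, item 2).
- Draw window: 21 days before registration by default (Section 5.2), or 7 days if drawn with the screening CBC/CMP (footnote 9 with Section 5.2).
- Lag from registration to Day 1: not stated. Assumed values are 0, 3 and 7 days.

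**Formula.** For a screening draw, shortest time from last therapy to draw = 28 − draw window − lag. A pre-dose Day 1 draw shares its anchor with the washout, so the lag drops out.

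| Baseline draw | Lag 0 | Lag 3 | Lag 7 |
|---|---|---|---|
| 21 days before registration | 28 − 21 = 7 | 4 | 0 |
| 7 days before registration | 28 − 7 = 21 | 18 | 14 |
| Cycle 1 Day 1, pre-dose | 28 | 28 | 28 |

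The table stops at 0 because Section 4.6 bars systemic chemotherapy during screening. The bar does not close the gap: therapy can end just before consent and the draw can follow within days.

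**Length of the paired interval.** Week 12 is day 84. With lag 0, the two samples are 84 + 21 = 105, 84 + 7 = 91 or 84 days apart for the three draw times, each ± 7 days.

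**What footnote 9 covers.** It specifies 30 ml. Section 5.5.1.2 takes about 20 ml for PBMCs and Section 5.5.1.3 about 10 ml for buffy coat: 20 + 10 = 30. The preference therefore appears to concern these two samples, which leaves EBV DNA on the 21-day default.

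**Direction, immune markers (assumed figures).** If a subset were 20% to 40% below its usual level at the draw and fully recovered by week 12, the paired ratio with no drug effect would be 1/0.80 = 1.25 to 1/0.60 = 1.67, an apparent rise of 25% to 67%.

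**Direction, EBV DNA (assumed figures).** If untreated EBV DNA doubled every 8 to 4 weeks, a draw 3 weeks early would understate the first-dose level by a factor of 2^(3/8) = 1.30 to 2^(3/4) = 1.68. The ratio of week 12 to baseline is inflated by that factor, so a true fall looks smaller. A baseline lowered by prior therapy acts in the same direction.

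Both illustrations show direction only. No suppression, recovery or doubling figure is in the documents.

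**The case against.** The strongest reply is that seven days is a corner case. It needs therapy to have ended at the edge of the washout, a draw on the first permitted day, and no use of footnote 9. With footnote 9 followed and no lag, the gap is 21 days, and a Day 1 draw then gains only 28 − 21 = 7 days. This stands as to how often the extreme will occur. It does not remove the problem, because footnote 9 is a preference and appears not to cover EBV DNA.

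Second, the markers are exploratory and Section 9.6 names no paired test. No sample size or decision rests on them, and an uncontrolled before/after comparison is limited whatever the baseline date. This stands and sets the weight of the point. Still, Section 2.3 does plan the comparison, and correlating markers with outcome is a secondary objective (Section 2.2).

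Third, a reader might infer that the lag from registration to first dose has no limit. The documents imply a loose one. Section 10.4 requires eligibility, including measurable disease, to be confirmed before registration, and Appendix A, 1.2.1, allows baseline evaluations no more than 4 weeks before treatment. That caps the lag at about 4 weeks, which is too wide to help.

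Fourth, a reader might extend the argument to tissue, collected "within 42 days of initiating study treatment", since a biopsy can precede the last permitted therapy. That is a separate matter. The repeat biopsy is optional, so there is no mandatory pair, and archival tissue is already accepted by exception.

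**Conclusion.** The point holds as a cheap improvement to the exploratory part of the trial. The documents allow a baseline PBMC or buffy-coat draw as little as 7 days after chemotherapy or radiotherapy if registration is on Day 1, or about 21 days under the preferred timing; a registration-to-dose lag shortens both. In a single arm with no planned adjustment, recovery can then be mistaken in part for immune activation.

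Three stronger readings are not supported:
- That EBV DNA recovery would pass for an avelumab effect. A baseline that is too low masks a fall, and EBV DNA is followed serially rather than as one pair.
- That the bias is known to be large. Only the date arithmetic comes from the documents; the size of the effect and the share of patients sampled early are unknown.
- That the trial's main conclusion is at risk. The response endpoint, the Simon boundaries and the safety analyses do not use these samples.

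For radiotherapy there is a further uncertainty: Section 3.2 permits prior palliative radiotherapy without making clear whether the 4-week limit applies to it.

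**What to change.** 1. In Sections 5.2, 5.3.1, 5.5.1.2 and 5.5.1.3 and the Schedule of Events (footnotes 7 and 9 included), take the baseline PBMC, buffy-coat and EBV DNA blood on Cycle 1 Day 1 before the first infusion, with the CBC/CMP already drawn there. State the pre-dose requirement explicitly.
2. Record the date of last anticancer therapy and derive the days from it to the draw.
3. In Section 9.6, show the paired changes and the baseline-marker models by, or adjusted for, that interval. This is needed even after step 1, because a Day 1 sample may still be only 28 days after therapy: the confounding is reduced, not removed. With at most 39 patients, a single covariate or a simple split is enough.
4. For tissue, add at most a sensitivity analysis that excludes biopsies followed by anticancer therapy before the first dose.

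**Cost.** There is no extra sample or visit, and neither EBV DNA level nor any correlative result is an eligibility criterion, so nothing is needed earlier. The downside is that a missed pre-dose draw cannot be repeated, whereas a missed screening draw can. Registered patients who are never dosed would give no blood, but they could not contribute a pair.

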5.5.1.3 Buffy Coat

Blood samples will be collected in one EDTA purple top tube (approximately 10 ml) prior to study treatment at screening (may be collected at the same time as blood drawn for routine laboratory tests).

Additional blood samples will be collected in one EDTA purple top tube (approximately 10 ml) at:

time of first radiographic disease assessment 12 weeks after treatment initiation, (± 7 days)

Samples should be processed the day of collection according to the buffy coat isolation protocol in the Laboratory Manual.

Samples should be stored at -80°C until shipment.

5.5.3 Specimen Analyses

Analyses will be performed at the direction of the study chair, [name].

Tumor specimens will be evaluated by immunohistochemistry (IHC) for such biomarkers as:

- PD-L1 expression
- T cell subsets (CD4, CD8, FOXP3)
- Macrophage (CD68)

• Cytokeratin 5/6

PBMCs will be analyzed by flow cytometry for the following immune cell markers:

- T cell subsets (CD3, CD4, CD8, CD25, FOXP3)
- B cells (CD 19, CD20)
- Macrophage I/II and myeloid-derived suppressor cells (MDSC) (CD16, CD68, CD206),
- Natural killer cell activity (CD56, CD16)

Buffy coat samples will be analyzed for T cell receptor (TCR) and B cell receptor (BCR) sequencing.

EBV DNA plasma levels will be evaluated in peripheral blood at baseline, then every 12 weeks after treatment initiation and at end of treatment.

Fresh frozen core biopsies (when available) will undergo whole exome sequencing for neoantigen discovery.

Additional biomarkers may be examined as new information arises.

5.5.4 Specimen Banking

Patient samples collected for this study will be retained in the UCSD Moores Cancer Center Biorepository for analysis and future cancer research. Specimens will be stored indefinitely or until they are used up. Samples will be labeled with the protocol number, subject's de-identified study number and collection date. The link between study number and medical record number will be viewed over a password secured encrypted server-client.

The study research coordinator at each local site will review their subject's medical record for demographic and clinical information pertaining to the subject's general medical history, diagnosis, and outcomes of any treatments received. This information will be transmitted to and retained by the Coordinating Site UCSD. Samples and data extracted from the subject's medical record will be coded with a de-identified study number so that the subject's name and identifying information will be removed. A log that links the subject's name and identifiers to the study number will be maintained in a secure database distinct from the secure database into which the subject's clinical information will be entered by study personnel.

Dissemination of specimens for research is at the discretion of the Study Chair, [name]. Potential research collaborators outside of UCSD who approach the Moores Cancer Center for clinical specimens will be required to complete an agreement (Material Transfer Agreement or recharge agreement) stating that the specimens will only be released for use in disclosed research, and any specimen left over from research will either be returned to the Cancer Center or destroyed. Any data obtained from the use of clinical specimen will be the property of UCSD for publication and any licensing agreement will be strictly adhered to. These outside collaborators may include for-profit biotechnology corporations interested in collaborating with UCSD investigators in research diagnostic, prognostic assays and drug development.

The specimens, DNA, and their derivatives may have significant therapeutic or commercial value. The Informed Consent form contains this information and informs the subject that there is the potential for financial gain by UCSD, the investigator or a collaborating researcher or entity.

If patients later decide they do not want their specimens collected to be used for future research, they may tell this to the local site principal investigator, who will inform the Study Chair [name]. [name] will use her best efforts to stop any additional studies and to destroy the specimens. Samples stored in the Biorepository will be destroyed; for samples that have been disseminated outside of the Biorepository, [name] will contact the recipient to notify them of the need to halt further research and destroy specimens.

6.0 Measurement of Effect

6.1 Safety/tolerability

Analyses will be performed for all patients having received at least one dose of study drug. The study will use the CTCAE version 4.03 (http://ctep.cancer.gov/reporting/ctc.html) for reporting of adverse events.

6.2 Antitumor Effect

Response and progression will be evaluated in this study using the international criteria proposed by the Response Evaluation Criteria in Solid Tumors (RECIST) Committee [*JNCI* 92(3):205-216, 2000]. Changes in only the largest diameter (unidimensional measurement) of the tumor lesions are used in the RECIST v1.1 criteria. See Appendix A.

6.2.1 Best Overall Response

The best overall response is the best response recorded from the start of the study treatment until the end of treatment taking into account any requirement for confirmation.

6.2.2 Progression-Free Survival

Progression-free survival (PFS) is defined as the duration of time from start of treatment until objective tumor progression or death.

6.2.3 Time to Progression

Time to progression is defined as the duration of time from start of treatment until objective tumor progression.

6.2.4 Overall Survival

Overall survival is defined as the duration of time from start of treatment to death.

7.0 ADVERSE EVENTS

An adverse event (AE) is any untoward medical occurrence in a patient receiving study treatment and which does not necessarily have a causal relationship with this treatment. An AE can therefore be any unfavorable and unintended sign (including a clinically significant abnormal laboratory finding), symptom, or disease temporally associated with the use of an experimental intervention, whether or not related to the intervention. Any worsening (i.e., any clinically significant adverse change in frequency and/or intensity) of a preexisting condition that is temporally associated with the use of the investigational agent, is also an AE.

Progression of the cancer under study or events which are unequivocally due to disease progression should not be reported as an AE during the study (unless it is considered to be drug related by the investigator).

